### **6.9.2 Tumour Marker**

For subjects with an abnormal tumour marker strongly related to their tumours, the tumour marker will be measured. Sampling for tumour marker measurements will be performed according to [Table 5](#) and [Table 9](#).

Tumour markers will be measured at the study site or external laboratory in accordance with the standard procedure of each study site. The type of tumour markers and the dates of each measurement and collection will be recorded in the appropriate sections of CRF.

Date

## **7. EVALUATION AND CALCULATION OF VARIABLES AND STATISTICAL METHODS**

### **7.1 Definition of study endpoints**

To meet the objectives for this study, data for the following endpoints will be collected:

- Safety and Tolerability (Primary)
- MTD and/or optimal biologic dose, if possible (Secondary)
- MEDI-573 PK (Secondary)
- IM (Secondary)
- Pharmacodynamics (Secondary)
- MEDI-573 Tumour response (Secondary)
- Exploratory biomarkers (levels of circulating soluble protein biomarkers including GH, IGF1, insulin and glucose, and levels of phosphorylated and/or factors biomarkers in specimens including IGF-1R, IRS-1, MAPK, ERK, Ki67, caspase 3, and/or AKT) (Exploratory)
- Pharmacogenetics (Exploratory)

Safety endpoints are defined in Sections 6.3 and 6.4. Calculations and analysis plans for each of these endpoints are presented below.

### **7.2 Determination of sample size**

The primary objective of this study is to investigate the safety and tolerability and thereby identify the MTD of MEDI-573. Hence the number of subjects has been based on the desire to obtain adequate tolerability, safety and pharmacokinetic and PK data while exposing as few patients as possible to the investigational product and procedures.

For each cohort, cohorts of 3-6 evaluable subjects will be required. The total number of subjects will depend upon the number of dose escalations necessary.

### **7.3 Calculation or derivation of safety variables**

Safety and tolerability will be assessed in terms of AEs, laboratory data, vital signs and ECG changes. These will be collected for all subjects.

#### **Creatinine Clearance**

CrCl will be calculated using the Cockcroft-Gault formula ([Cockcroft and Gault 1976](#)) as follows:

Date

For Women:

$$\text{CrCl} = \frac{\{[140 - \text{Age (years)}] \times \text{Mass (kg)} \times 0.85\}}{\{72 \times \text{serum creatinine (mg/dL)}\}}$$

OR

$$\text{CrCl} = \frac{\{[140 - \text{Age (years)}] \times \text{Mass (kg)} \times 0.85\}}{\{815 \times \text{serum creatinine (mmol/L)}\}}$$

For Men:

$$\text{CrCl} = \frac{\{[140 - \text{Age (years)}] \times \text{Mass (kg)}\}}{\{72 \times \text{serum creatinine (mg/dL)}\}}$$

OR

$$\text{CrCl} = \frac{\{[140 - \text{Age (years)}] \times \text{Mass (kg)}\}}{\{815 \times \text{serum creatinine (mmol/L)}\}}$$

### 7.3.1 Other significant adverse events

During the evaluation of the AE data, a medically qualified expert will review the list of AEs that were not reported as SAEs and AEs leading to discontinuation of investigational product. Based on the expert's judgement, AEs of particular clinical importance may, after consultation with the Global Safety Physician, be considered OAEs and reported as such in the Clinical Study Report. A similar review of laboratory values, vital signs, ECGs and other safety assessments will be performed for identification of OAEs.

Examples of these are marked haematological and other laboratory abnormalities, and certain events that lead to intervention (other than those already classified as serious), dose reduction or significant additional treatment.

## 7.4 Calculation or derivation of pharmacokinetic variables

PK analysis of the serum concentration data for MEDI-573 will be performed by AstraZeneca K.K. The actual sampling times will be used in the parameter calculations and PK of MEDI-573 will be assessed by noncompartmental approach using a validated computer software package WinNonlin®. Descriptive statistics will be provided by dose cohort.

$C_{\max}$ ,  $C_{\max}$  at steady state ( $C_{\max, ss}$ ), time to maximum concentration ( $t_{\max}$ ) and the  $t_{\max}$  at steady state ( $t_{\max, ss}$ ) will be determined by inspection of the concentration-time profiles. Where possible the terminal elimination rate constant ( $\lambda_z$ ) after first dose will be calculated by log-linear regression of the terminal portion of the concentration-time profiles where there are sufficient data and the elimination half-life at terminal phase ( $t_{1/2\lambda}$ ) will be calculated as  $\ln 2/\lambda_z$ .

Date

The area under the curve up to the last quantifiable sample ( $AUC_{(0-t)}$ ) will be calculated using the linear trapezoidal rule. Where appropriate, the  $AUC_{(0-t)}$  will be extrapolated to infinity using  $\lambda_z$  to obtain AUC. Total clearance (CL; following the first dosing) will be determined from the ratio of dose/AUC. The volume of distribution at terminal phase ( $V_z$ ) will be determined from the mean residence time (MRT) x CL and/or the accumulation ratio ( $R_{ac}$ ) will be calculated as the ratio of the  $C_{max}$  and  $C_{min}$  on last dosing interval and first dosing interval.

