### **3.1 Overall study design and flow chart**

#### **Study Design**

This is a Phase 1, open-label, single-arm, dose-escalation study to evaluate the safety, tolerability, and pharmacokinetics of MEDI-573 in Japanese adult patients with advanced solid tumours refractory to standard therapy or for which no standard therapy exists.

The study will be conducted at one site in Japan.

Subjects are considered evaluable if they receive 3 doses of MEDI-573 (Cohorts 1 and 2) or 1 dose of MEDI-573 (Cohort 3) during cycle 1 and are followed for 21 days from the date of first dose (one cycle) or they discontinue MEDI-573 due to dose-limiting toxicities (DLTs). Each cohort will include 3 to 6 evaluable subjects and a total of 9 to 18 evaluable subjects will be evaluated during the study.

MEDI-573 will be administered once every 7 days (on Days 1, 8, and 15 of each 21-day treatment cycle) as a 60-minute IV infusion in Cohorts 1 and 2 and once every 21 days (Day 1 of each 21-day treatment cycle) as a 90-minute IV infusion in Cohort 3 until unacceptable toxicity, documentation of disease progression, or other reasons for subject withdrawal. Intra-subject dose escalation will not be allowed. On 2nd Cycle and beyond, continuation, interruption or permanent discontinuation of treatment will be decided based on the criteria specified in section 5.1.8. Subjects will be considered to have completed a cycle only when they have received all the specified doses at each cycle, and subjects who do not complete a cycle will discontinue the treatment and not move on to the next cycle. Rules for interruption or discontinuation of MEDI-573 in individual subjects are described in Section 5.4.1. Rules for interruption or discontinuation of MEDI-573 and study entry are described in Section 5.4.2.

Dose escalation will follow a standard 3+3 design. Rules for dose escalation are described in Section 5.1.3.

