**Table 13**                      **Pharmacokinetic and Pharmacodynamics (Cohorts 1 and 2)**

Time for blood samples			PK	Biomarkers	
			573	antibodies	
Cycle 1	Day 1	Pre-dose	X	X	X
		End of infusion (+5 min)	X		X
		2 h after dose ( $\pm 15$ min)	X		X
		6 h after dose ( $\pm 15$ min)	X		X
	Day 2	24 h after dose of Day 1 ( $\pm 2$ h)	X		X
	Day 3	48 h after dose of Day 1 ( $\pm 2$ h)	X		X
	Day 8	Pre-dose	X		X
		End of infusion (+5 min)	X		X
	Day 15	Pre-dose	X		X
		End of infusion (+5 min)	X		X
Cycle 2	Day 1	Pre-dose	X	X	X
		End of infusion (+5 min)	X		X
	Day 8	Pre-dose	X		X
		End of infusion (+5 min)	X		X
	Day 15	Pre-dose	X		X
		End of infusion (+5 min)	X		X
Cycle 3 and beyond	Day 1	Pre-dose	X	X	X
		End of infusion (+5 min)	X		X
End of treatment			X		X
30 days after the last dose			X	X	X
3 months after the last dose				X	

Date

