**Table 14 Pharmacokinetic and Pharmacodynamics (Cohort 3)**

Time for blood samples			PK	Biomarkers	
			573 antibodies		
Cycle 1	Day 1	Pre-dose	X	X	X
		End of infusion (+5 min)	X		X
		2 h after dose ( $\pm 15$ min)	X		X
		6 h after dose ( $\pm 15$ min)	X		X
	Day 2	24 h after dose of Day 1 ( $\pm 2$ h)	X		X
	Day 3	48 h after dose of Day 1 ( $\pm 2$ h)	X		X
	Day 8	168 h after dose of Day 1 ( $\pm 2$ h)	X		X
	Cycle 2 and beyond	Day 1	Pre-dose	X	X
End of infusion(+5 min)			X		X
End of treatment			X		X
30 days after the last dose			X	X	X
3 months after the last dose				X	

The timing of the PK samples may be adjusted during the study, dependent on emerging data, in order to ensure appropriate characterisation of the plasma concentration-time profiles. The total number of samples and the total volume of blood taken from each subject will not exceed that presented in Section 6.8.1.

Collection, labelling, storage and shipment of the samples will be done in accordance with the Laboratory Manual.

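### Later doses have only one post-dose PK sample, so tmax,ss is in effect set by the schedule and the Cmax-based accumulation ratio is biased downward

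*Protocol*

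**What the plan says.** Section 7.4 plans a noncompartmental analysis. Cmax, Cmax,ss, tmax and tmax,ss "will be determined by inspection of the concentration-time profiles", and "The actual sampling times will be used in the parameter calculations". Rac is the ratio of Cmax and of Cmin "on last dosing interval and first dosing interval".

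Tables 13 and 14 fix the samples. In all cohorts the first dose is sampled before dosing, at end of infusion, and at 2, 6, 24 and 48 h (the 24 h row reads "24 h after dose of Day 1"). Cohort 3 adds "168 h after dose of Day 1"; in Cohorts 1 and 2 the next sample is the Day 8 pre-dose one. Every later dose that is sampled at all has two samples, pre-dose and end of infusion.

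Section 6.5.1 adds, after Table 14: "The timing of the PK samples may be adjusted during the study, dependent on emerging data". The total number of samples and the blood volume are capped there at the figures in Section 6.8.1.

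**The concern.** One derivation rule is applied to two kinds of profile. For the first dose the rule picks the largest of several post-dose values. For a later dose there is only one value around the peak to pick.

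Two things follow. First, tmax,ss cannot show when the peak occurs, because no other time after the start of a later infusion is sampled near the peak. Second, the maximum of several similar values measured with error is on average higher than any one of them. First-dose Cmax carries that upward selection and Cmax,ss does not. Section 7.4 then divides one by the other in Rac.

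Describing the pharmacokinetics is the first secondary objective (Section 1.2). Peak accumulation would tend to read too low, and a difference between tmax and tmax,ss could reflect sampling density alone.

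**Working it through.** **Step 1: the schedule against the protocol's own counts.** Counting PK rows in Tables 13 and 14:

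- Cohorts 1 and 2, Cycle 1: 4 (Day 1) + 1 (Day 2) + 1 (Day 3) + 2 (Day 8) + 2 (Day 15) = 10. Cycle 2: 3 × 2 = 6. Cycle 3 and beyond: 2.
- Cohort 3, Cycle 1: 4 + 1 + 1 + 1 = 7. Cycle 2 and each later cycle: 2.

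Tables 16 to 18 in Section 6.8.1 give 10, 6 and 2 (Cohort 3: 7, 2 and 2). All six cells agree, so the single post-dose sample at later doses is the intended schedule.

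**Step 2: tmax,ss.** For a later dose the observed maximum is the end-of-infusion sample, at about 1 h in Cohorts 1 and 2 and 1.5 h in Cohort 3. The exception is a pre-dose reading that exceeds it through measurement error. With error CV c, σ = √ln(1+c²) and a trough that is a fraction r of the peak, the chance of that is 1 − Φ(−ln r / (σ√2)). For r = 0.5 it is 0.7% at 20% CV. For r = 0.8 it is 5.7% at 10% CV and 21% at 20% CV. Either way, the result says nothing about when the drug peaks.

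**Step 3: bias in the Cmax part of Rac.** The protocol gives no assay CV and no human half-life, so these inputs are assumed. The level relative to end of infusion, t hours later, is

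s(t) = (1 − f)·2^(−t/T) + f·2^(−t/6),

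with terminal half-life T of 3, 7, 14 or 21 days, fast-distribution fraction f of 0, 0.15 or 0.30, and a 6 h distribution half-life. Samples are at t = 0, 2, 6, 24 and 48 h, with log-normal error of CV 5 to 20% and 200,000 profiles per setting. The nominal hours are taken as counted from end of infusion. The ratio is the geometric mean of a single end-of-infusion value over the geometric mean of the five-sample maximum, with the true peaks equal; the right answer is 1.

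Each cell gives the ratio, then the share of first-dose profiles with tmax at end of infusion:

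| T, f | CV 5% | CV 10% | CV 20% |
|---|---|---|---|
| 21 d, 0 | 0.957; 31% | 0.906; 26% | 0.810; 23% |
| 7 d, 0 | 0.967; 42% | 0.924; 35% | 0.833; 29% |
| 7 d, 0.15 | 0.986; 68% | 0.953; 52% | 0.873; 40% |
| 3 d, 0 | 0.977; 54% | 0.939; 44% | 0.860; 36% |
| 3 d, 0.30 | 0.995; 87% | 0.973; 69% | 0.910; 53% |

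Over the whole grid the ratio runs from 0.810 to 0.995 and the tmax share from 23% to 87%. A 3 h distribution half-life takes the mildest case to 0.999 and 97%. As a check, five exactly equal levels give exp(−1.163σ), where 1.163 is the expected maximum of five standard normals. At 20% CV σ = 0.198 and the ratio is 0.794, a floor that the simulated values respect.

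Dividing end of infusion by end of infusion gives 1.00 in every setting, because both terms have the same expectation.

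**Step 4: what it does to Rac.** For one-compartment decline, true peak accumulation is 1/(1 − 2^(−τ/T)). With T = 7 d and f = 0:

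- Weekly dosing: 1/(1 − 0.5) = 2.00. At 20% CV this reads as 2.00 × 0.833 = 1.67.
- Dosing every 21 days: 1/(1 − 0.125) = 1.14. At 10% CV this reads as 1.14 × 0.924 = 1.06, and at 20% CV as 1.14 × 0.833 = 0.95.

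**The case against.** The drug is given by constant infusion, so the true peak is expected at the end of it. That sample is taken at every dose with the same window, so Cmax,ss estimates the right quantity. This stands. It rules out the stronger reading that the two peaks cannot be compared at all. They can be, from end-of-infusion samples, but Section 7.4 does not ask for that comparison.

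The size is not anchored in the documents. The only PK figures are from monkeys. Taking volume as dose/Cmax, they suggest a half-life of about 2.9 days (60,000/1643 = 36.5 mL/kg; 0.693 × 36.5/8.67) or 2.5 days (60,000/1343 = 44.7 mL/kg; 0.693 × 44.7/12.6). With low assay error and marked early distribution the bias is negligible. This stands too, and is why a range is given.

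A reader might infer that the report will show tmax moving earlier at steady state. That is possible, not certain. Section 7.9 summarises with the mean, median and range. Where more than half of first-dose profiles peak at end of infusion, the median would usually not move, and each cohort has only 3 to 6 evaluable subjects.

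Sample times may be adjusted on emerging data, but the cap equals the present schedule. Samples could be moved to a later dose, not added. Nor is this a matter left open for the SAP: Section 7.4 states the rule, and the rule does not fit the protocol's tables.

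**Conclusion.** The point holds in limited form. That tmax,ss carries no information beyond the schedule follows from the protocol alone. So does the direction of the bias in the Cmax part of Rac, given any measurement error and a slow early decline.

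The size rests on assumption: an understatement from under 1% to about 19% for half-life 3 to 21 days, CV 5 to 20% and 0 to 30% fast distribution, with no setting reversing the direction. With weekly dosing and a half-life of a week or more, accumulation would still be plain. In Cohort 3, where true accumulation may be close to 1, the bias could hide it.

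The parameters are secondary and descriptive. The escalation rules in Section 5.1.3 rest on DLTs, the committee sees PK only if available, and the primary safety objective does not use these quantities.

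**What to change.** Change the wording of Section 7.4 only:

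- Delete tmax,ss, or label it as determined by the sampling schedule.
- Define Cmax,ss as the observed end-of-infusion concentration.
- Compute the Cmax part of Rac from end-of-infusion samples in both the first and the last interval.
- Keep Cmax and tmax as they are for the serially sampled first dose.

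The end-of-infusion samples already exist at each sampled dose, so there is no extra blood, visit or patient. If a real steady-state tmax is wanted, existing samples would have to be moved to a later dose within the Section 6.8.1 cap, at the expense of what they now measure.

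### First-dose clearance and half-life come from a 7-day curve in Cohorts 1 and 2 but a curve of about 21 days in Cohort 3, so the planned calculation makes clearance look lower in Cohort 3 even when it is the same

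*Protocol*

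**What the plan says.** Protocol section 7.4 sets out a noncompartmental analysis. The terminal slope "after first dose will be calculated by log-linear regression of the terminal portion of the concentration-time profiles where there are sufficient data", and half-life is ln 2 divided by that slope. AUC to the last quantifiable sample "will be calculated using the linear trapezoidal rule". Where appropriate, it "will be extrapolated to infinity using" the terminal slope. Then "Total clearance (CL; following the first dosing) will be determined from the ratio of dose/AUC". For reporting, "Descriptive statistics will be provided by dose cohort".

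The dosing schedule (section 3.1) fixes how long a first-dose curve can be. Cohorts 1 and 2 are dosed "once every 7 days (on Days 1, 8, and 15 of each 21-day treatment cycle"). Cohort 3 is dosed once per 21-day cycle.

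The sampling tables match at the start: pre-dose, end of infusion, then 2, 6, 24 and 48 h. After that:

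- **Cohorts 1 and 2 (Table 13):** after the sample at "48 h after dose of Day 1", the next is the Day 8 pre-dose sample, immediately before the second dose.
- **Cohort 3 (Table 14):** there is a sample at "168 h after dose of Day 1", and the next is the Cycle 2 Day 1 pre-dose sample, at about 504 h.

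**The concern.** One set of rules is applied to first-dose curves of very different length. Two mechanisms follow, and both depend on the cohort.

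1. **The window.** In Cohorts 1 and 2 the last three points are at about 24, 48 and 168 h. If distribution is still under way at 24 to 48 h, the fitted slope is too steep. The extrapolated area is then too small and clearance too high. In Cohort 3 the last three points are at about 48, 168 and 504 h, which lie much further into the terminal phase.
2. **The linear rule.** A straight line across an exponential decline overstates area, and so understates clearance. The longest interval is 120 h in Cohorts 1 and 2 and 336 h in Cohort 3.

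Describing the pharmacokinetics is the first secondary objective. Dose and schedule both change on the step to Cohort 3 (Table 2), so an artefact of the calculation could be taken for dose-dependent clearance or a regimen effect, or could mask one.

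**Working it through.** The protocol gives no human clearance or half-life, so there is no figure of its own to reproduce. The check applies the section 7.4 rules to error-free first-dose curves with the same true clearance in every cohort.

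**Inputs from the protocol**
- Infusion of 60 min in Cohorts 1 and 2, and 90 min in Cohort 3.
- Sample times from Tables 13 and 14, with 2, 6, 24 and 48 h counted from the end of infusion. The last point is 168 h in Cohorts 1 and 2 and 504 h in Cohort 3.

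**Assumptions**
- Terminal half-life of 2.5 to 21 days. The lower end is close to what the monkey data imply with one compartment: V = 60,000/1343 = 44.7 mL/kg and CL = 12.6 mL/day/kg give ln 2 × 44.7/12.6 = 2.5 days.
- Either one compartment, or two compartments with a 1-day distribution half-life and 55% of the initial concentration in the terminal phase.
- Terminal slope fitted to the last three points.

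**Formulas**
- AUC = linear-trapezoid AUC(0-t) + C(last)/λz
- CL = dose/AUC
- Bias = estimated CL/true CL − 1

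**The linear rule by hand (one compartment, 7-day half-life).** From 168 to 504 h is 14 days, or two half-lives, so concentration falls from C to 0.25C.
- Straight line: (1 + 0.25)/2 × 14 = 8.75 C·days.
- True area: 0.75 × 14/ln 4 = 7.57 C·days.
- True total AUC, measured from time 0, is about 2C/λz = 2 × 10.1 = 20.2 C·days.
- Excess from this one interval: (8.75 − 7.57)/20.2 = 5.8% of AUC. Adding about 0.6% from the earlier intervals gives a clearance bias of about −6%, matching the −6.1% in the table.

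**Bias in CL under section 7.4 as written**

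| Model | Half-life (days) | Cohorts 1 and 2 | Cohort 3 | CL ratio, Cohort 3 to Cohorts 1 and 2 (truth 1.00) |
|---|---|---|---|---|
| One compartment | 2.5 | −6.3% | −17.4% | 0.88 |
| | 5 | −1.5% | −10.0% | 0.91 |
| | 7 | −0.6% | −6.1% | 0.94 |
| | 10 | −0.3% | −3.1% | 0.97 |
| | 14 | −0.1% | −1.5% | 0.99 |
| | 21 | 0.0% | −0.5% | 0.995 |
| Two compartments | 2.5 | −7.9% | −18.0% | 0.89 |
| | 5 | +5.0% | −11.2% | 0.84 |
| | 7 | +14.5% | −6.9% | 0.81 |
| | 10 | +28.9% | −2.3% | 0.76 |
| | 14 | +48.4% | +2.1% | 0.69 |
| | 21 | +82.9% | +8.8% | 0.59 |

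The ratio is below 1 in all 12 scenarios. The shortfall is 0.5 to 12% with one compartment and 11 to 41% with two.

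**Half-life and extrapolation.** For a true 14 days in the two-compartment case, the estimated half-life is 6.9 days in Cohorts 1 and 2 and 12.0 days in Cohort 3. The extrapolated share of AUC is 49% and 29%. In the one-compartment case at 14 days the shares are 71% and 35%.

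**Candidate remedies on the same curves**
- **Linear-up/log-down:** the one-compartment bias becomes 0% in every cohort. With two compartments, Cohort 3 falls to between −1.8% and +9.6%, but Cohorts 1 and 2 stay at +0.2% to +84%. The rule change does not remove the window effect.
- **Cutting the Cohort 3 curve at 168 h:** its bias then matches Cohorts 1 and 2 within about 0.2 points (two compartments, 10 days: +29.0% against +28.9%). Clearance is then comparable but still biased.
- **Dose-normalised AUC(0-7 d):** Cohort 3 and Cohorts 1 and 2 agree within about 0.2% in all scenarios.

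**The case against.** **The text is conditional.** The slope is fitted only where data suffice, extrapolation is done only where appropriate, the PK analysis set (Table 20) requires an adequate profile, and sample times may be adjusted. This is true, but it does not prevent the artefact. Points at 24, 48 and 168 h give a fitted slope, and no change of sample times can carry the weekly first-dose curve past the Day 8 dose. Numerical acceptance limits on extrapolation belong in a SAP or PK plan, so their absence is not part of this point.

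**The 504 h sample is listed under Cycle 2.** Section 7.4 does not say that it belongs to the first-dose profile. That it does is the natural reading, but it is an inference, and the size of the cohort gap rests on it. A subject who does not enter Cycle 2 would lack that sample.

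**The size depends on the model.** This stands. With one compartment and a half-life of 14 days or more, the gap is under 2%. The large figures need a distribution phase that the protocol neither describes nor excludes.

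**Stronger readings to avoid.** A reader might infer that the two biases run in opposite directions. They do so only in the middle of the two-compartment range. With one compartment, both are negative or nil. With two, both are negative at 2.5 days and both positive at 14 and 21 days.

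A reader might also infer that dose escalation could be misled. The documents do not support that. Escalation in section 5.1.3 rests on DLTs, the dose escalation committee sees PK only if possible, Cohort 3 is the last in Table 2, and its dose is set from Study MI-CP184. Cohorts 1 and 2 share a schedule, so no window artefact arises between them. Section 7.4 plans descriptive statistics, with no test across regimens.

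**Conclusion.** The point holds at a moderate level. Section 7.4 fixes first-dose clearance, a first-dose terminal slope and the linear trapezoid. Combined with Tables 13 and 14 and the redosing days, these make clearance look lower in Cohort 3 when it is the same in all cohorts. The direction was constant in every scenario tried.

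The size is not established: 0.5 to 12% with one compartment, and 11 to 41% with the assumed two-compartment model, over an assumed half-life of 2.5 to 21 days. All of these figures assume linear pharmacokinetics, error-free concentrations, a three-point slope, and use of the 504 h sample in Cohort 3. The consequence is a possible misreading of descriptive secondary results. The primary safety conclusion is unaffected, as is every listed escalation step.

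**What to change.** Amend section 7.4 in two places.

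1. Replace the linear trapezoidal rule with linear-up/log-down. This removes the one-compartment bias and most of the Cohort 3 bias at short half-lives. It does not remove the window effect in Cohorts 1 and 2, so it is not enough alone.
2. State that any comparison between the weekly and three-weekly cohorts will use dose-normalised AUC(0-7 d), which every cohort has at the same nominal times. Present first-dose clearance and half-life with the extrapolated share of AUC, and say that they are not comparable across regimens. State also whether the Cycle 2 Day 1 pre-dose sample closes the Cohort 3 first-dose profile.

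A compartmental or population fit to all collected samples would be a useful supplement, but it is optional.

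The cost is slightly more PK reporting, and first-dose clearance in the weekly cohorts will carry a caveat. No extra blood, samples or visits are needed.

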SAE	Serious adverse event (see definition in Section 6.4.2)
SAS	Statistical Analysis System
SD	Stable disease
SID	Subject Identification Number
t 1/2	Elimination half-life at terminal phase
t max	Time to maximum serum concentration
t max,ss	t max at steady state
TSH	Thyroid stimulation hormone
TTP	Time to progression
TTR	Time to response
TUNEL	Triphosphate biotin nick end labeling
ULN	Upper limit of normal
US	United States
V z	Volume of distribution at terminal phase
WBDC	Web Based Data Capture
WHO	World Health Organization
λ z	Terminal elimination rate constant

---

Date

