**Table 2 Summary of Dose Cohorts**

Dose Cohort	Number of Subjects	MEDI-573 Dose
1	3-6	5.0 mg/kg as a 60-minute IV infusion once every 7 days
2	3-6	15 mg/kg as a 60-minute IV infusion once every 7 days
3	3-6	30 or 45 mg/kg as a 90-minute IV infusion once every 21 days

Subjects will be enrolled to ensure a minimum of 3 and a maximum of 6 evaluable subjects per cohort. Dose escalation will follow the scheme below, according to the following logic:

If no DLT is observed (for definition see Section 5.1.4) in a cohort of 3 evaluable subjects, then dose escalation may occur. Dose increases will be permitted after review of data from a minimum of 3 evaluable subjects has been performed.

If one subject of the 3 evaluable subjects experiences a DLT, then 3 more evaluable subjects will be enrolled to have 6 evaluable subjects. If only one DLT is observed in the complete cohort of 6 evaluable subjects, then dose escalation may occur.

If 2 or more subjects experience a DLT in a group of up to 6 subjects, irrespective of the number of subjects enrolled, the dose will be considered not tolerated and recruitment to the cohort and dose escalation will cease. If the next lower dose level has 3 evaluable subjects, 3 more evaluable subjects will be enrolled to have 6 evaluable subjects.

At the discretion of the sponsor, an intermediate dose may be chosen for dose escalation. Situations that might prompt selection of an intermediate dose include unexpected toxicities that do not meet the definition of DLT or multiple similar toxicities in a cohort that do not meet the definition of a DLT. If an intermediate dose is chosen, subsequent dose escalation will be to the next predetermined dose provided all the criteria for dose escalation in Rules above are met. Further dose escalation will be based on toxicities observed at each dose level,

Date

and may proceed according to the original dosing schedule or may include additional intermediate dosing steps based on accumulated safety data.

There will be no intra-subject dose escalations.

The dose for subsequent cohorts or a decision to stop recruitment will be agreed by the dose escalation committee (DEC) after review of the data from each cohort (see Section **Error! Reference source not found.**).

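### Section 7.4 labels MRT x CL as the terminal-phase volume Vz, but that product is the steady-state volume Vss

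*Protocol*

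**What the plan says.** Section 7.4 of the protocol has PK "assessed by noncompartmental approach using a validated computer software package WinNonlin". It then sets out these derivations:

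- λz after the first dose, where the data allow, "will be calculated by log-linear regression of the terminal portion of the concentration-time profiles", with the half-life taken as ln 2/λz.
- AUC to infinity by extrapolation with λz, where appropriate.
- CL after the first dose, which "will be determined from the ratio of dose/AUC".
- Vz, which "will be determined from the mean residence time (MRT) x CL".

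The abbreviation list defines Vz as "Volume of distribution at terminal phase", the same meaning as in Section 7.4. Neither a steady-state volume nor the symbol Vss appears anywhere in the protocol. The sentence on Vz also contains the accumulation ratio, joined to it by an and/or.

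**The concern.** The name and the formula describe two different parameters. Section 7.4 already derives CL and λz, the two quantities a terminal-phase volume needs, yet it does not use λz for Vz. It uses MRT, which leads to the steady-state volume.

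An analyst must then either follow the formula and report a Vss-type value as Vz, or report the usual Vz and depart from the protocol. If the formula is followed, the PK table would not be consistent within itself: Vz multiplied by λz should return CL, and it would not. A reader who uses the tabulated volume with the half-life or clearance would be misled about what it represents.

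**Working it through.** The protocol states no numerical volume, so there is no figure to reproduce. The check is algebraic, followed by an illustration of size.

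**Step 1: the two definitions.** For linear disposition after intravenous dosing:

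- Vss = CL × MRT
- Vz = CL/λz = Dose/(AUC × λz)

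Hence (MRT × CL)/Vz = MRT × λz. The ratio is 1 only if MRT = 1/λz. For a sum of declining exponentials with positive coefficients, MRT is an AUC-weighted average of the 1/λi. None of these exceeds 1/λz, because λz is the slowest rate. So the ratio is at most 1, with equality for a mono-exponential decline. The planned analysis is noncompartmental, so the plan makes no one-compartment assumption that would equate the two.

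**Step 2: illustrative size.** Take a two-compartment model with elimination from the central compartment:

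- s = CL/V1 + Q/V1 + Q/V2
- p = (CL/V1) × (Q/V2)
- λz = [s − √(s² − 4p)]/2
- Vss = V1 + V2, and Vz = CL/λz

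Inputs. Clearances of 8.67 and 12.6 mL/day/kg are the cynomolgus monkey means in Section 2.2.1. V1 of 40–45 mL/kg is assumed, and is of the same order as dose over mean monkey Cmax at 60 mg/kg: 60,000/1643 = 36.5 and 60,000/1343 = 44.7 mL/kg. V2 = 40 mL/kg, Q = 8–15 mL/day/kg and the lower clearance of 3.5 mL/day/kg are pure assumptions.

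| V1 | Q | CL | s | p | λz (/day) | MRT × CL = V1 + V2 | Vz = CL/λz | Gap |
|---|---|---|---|---|---|---|---|---|
| 45 | 15 | 3.5 | 0.7861 | 0.02917 | 0.03904 | 85.0 | 89.6 | −5.2% |
| 40 | 8 | 8.67 | 0.6168 | 0.04335 | 0.08090 | 80.0 | 107.2 | −25.4% |
| 40 | 8 | 12.6 | 0.7150 | 0.06300 | 0.10293 | 80.0 | 122.4 | −34.6% |

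The first and last rows are the extremes over the stated ranges, so the gap runs from about 5% to 35%. A wider assumed grid (V1 40; V2 20, 40 or 80 mL/kg; Q 3, 8 or 20 mL/day/kg; CL 3, 8.67 or 12.6 mL/day/kg) gives ratios of 0.28 to 0.98, a gap of about 2% to 72%. MRT × CL was below Vz in every two-compartment setting.

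**Step 3: consistency within the table.** In the middle row MRT = 80/8.67 = 9.23 days, while 1/λz = 12.36 days. The value reported as Vz, multiplied by λz, gives 80 × 0.0809 = 6.47 mL/day/kg, against a CL of 8.67 mL/day/kg.

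**Step 4: infusion time.** Table 2 gives "5.0 mg/kg as a 60-minute IV infusion once every 7 days" for Cohort 1, the same infusion time for Cohort 2, and "30 or 45 mg/kg as a 90-minute IV infusion once every 21 days" for Cohort 3. If MRT is not reduced by half the infusion time T, MRT × CL is inflated by CL × T/2:

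- CL 3.5, T = 1/24 day: 0.07 mL/kg
- CL 12.6, T = 1.5/24 day: 0.39 mL/kg

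This is negligible against volumes of 80 mL/kg or more, and it did not reverse the direction in any two-compartment setting.

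**The case against.** The mismatch itself is hard to dispute: the text is complete, the label appears in two places, and nothing elsewhere corrects the formula. The case on the other side is about how much follows from it, and most of it stands.

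- **Always smaller?** A reader might infer that the reported volume must fall below Vz. It need not. Under a mono-exponential decline the two are equal. An uncorrected infusion MRT would then make the product slightly larger: with an assumed volume of 60 mL/kg, at most 60.39, under 1%.
- **A firm size?** Selected pairings of V1 and Q from the Step 2 ranges can suggest a narrow gap such as 10% to 18%. The full ranges do not support that, and they rest on monkey clearances and assumed values. The 1343 µg/mL Cmax is from a weekly 13-week study and is not stated to be a first-dose value, so reading it as a central volume is uncertain.
- **Comparison with the US study?** One might conclude that the result could not be set beside a Vz from MI-CP184. The protocol does not say whether that study reports Vz or how it derives it.
- **Dose decisions?** Section 5.1.7 has the dose escalation committee look at PK data if possible, but no DLT, escalation, MTD or sample-size rule uses a volume of distribution. AUC, CL, λz and half-life are unaffected.
- **Which element is wrong?** The formula may be what was intended and the label the slip. The protocol does not settle this.

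**Conclusion.** The point holds as a definitional error. Section 7.4 gives the formula for Vss under the name Vz. That rests on the standard noncompartmental identities and on no assumed number.

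The direction is that MRT x CL is smaller than or equal to Vz, apart from the trivial infusion term. The size cannot be fixed from the protocol. The illustration of about 5% to 35% depends wholly on the assumed two-compartment values, and the wider grid shows how far it moves when they change.

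The consequence is limited to one descriptive parameter under the secondary PK objective, which would be misnamed and inconsistent with the CL and λz beside it. The documents do not support extending it to the safety conclusions or dose selection. It should be corrected because the stated rule is wrong as written and the repair is easy.

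**What to change.** Decide which volume is wanted and make name and formula agree. Either:

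1. keep the name and write Vz = CL/λz, reported where λz can be estimated; or
2. keep the formula, write it as CL × (MRT − T/2) with T the infusion duration, and rename the parameter Vss in Section 7.4 and in the abbreviation list.

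Both may be reported if each has its own name. In the same edit, give the accumulation ratio its own sentence, so that the and/or no longer leaves it unclear whether both quantities are required.

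The cost is a line or two of protocol text, plus the same wording in the statistical analysis plan if it repeats the formula. No extra samples, visits or subjects are needed, because all the quantities come from data already planned.
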